Grant Number: UH3DA047793

Title: tDCS to Decrease Opioid Relapse

MPIs: [name] and [name]

Medical Monitor: [name]

2. Summary of the Protocol:

2.a, 2.b Brief Description of the Protocol, Primary and Secondary Outcome Measures

This study has two phases. In phase one (UG3), we propose to use functional magnetic resonance imaging (fMRI) and electroencephalographic (EEG) to quantify changes in brain function and reported craving before and after administration of five sessions of transcranial direct current stimulation (tDCS) targeting the right dorsolateral prefrontal cortex (DLPFC). Opioid dependent participants (n=60) who recently initiated buprenorphine or methadone will be randomized to tDCS+Cognitive Control Network (CCN) priming stimulation vs. sham tDCS+CCN priming. Participants in their first month of prescribed buprenorphine or methadone will be assessed using fMRI and EEG, once prior to tDCS and again one week later after completion of 5 sessions of tDCS+CCN priming. With a focus on the craving outcome, we will use two task-based fMRI paradigms that challenge networks associated with craving (CR) and cognitive control (CCN), and will examine these and the salience network using resting state functional connectivity. We examine an additional validation measure of the effect of tDCS on the DLPFC – an oscillatory target -- EEG frontal theta power during working memory(WM). In this UG3 phase, fMRI and EEG will be expected to provide 1) validation of expected network and oscillatory changes from tDCS-targeting and 2) an effect size for DLPFC vs sham stimulation. Go/no go criteria for the UG3 phase will be demonstration of greater fMRI change in any node of the CR or CCN networks or enhanced frontal theta power during a WM task AND greater change (at least 10% difference between conditions, controlling for baseline craving) in subjective craving measured during a cue reactivity task or outside the fMRI following the tDCS+CCN priming intervention compared to sham tDCS+CCN priming.

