The optimal frequency, duration and number of tDCS sessions to maximize effects on craving, or any other construct in this young field, remain obscure. We chose to deliver 5 sessions of tDCS because this number has been used in prior successful tDCS craving interventions and must be balanced against adherence concerns. While we are hopeful that participants will complete 5 consecutive days of tDCS, the interruption of weekends and the transition from the ADP setting (where the tDCS protocol will start) where days are structured, to the community setting, raises the possibility of missed tDCS sessions and therefore we will allow these 5 sessions to occur over 10 days if necessary, as has been described in prior studies, tracking both average number of sessions received and period of treatment for analyses. The sham tDCS condition is included in our design to separate the effects of ongoing opioid treatment from the effect of active tDCS on craving. We decided not to include a third no-tDCS arm, as this would omit any nonspecific treatment effects (match for attention, expectation) of entering a neurostimulation treatment protocol. This protocol will provide a basis for future studies of tDCS stimulation parameters (frequency, duration, number) that could optimize adherence and treatment effects of drug use outcomes.

In phase two (UH3), we will perform a larger RCT using the same treatment protocol in 100 opioid dependent participants who recently initiated buprenorphine or methadone. Participants will be randomized to receive five sessions of tDCS+CCN priming stimulation vs. sham tDCS+CCN priming. Phase two will address long-term (3-month) neurobehavioral outcomes, including opioid relapse, craving, and sustained fMRI changes during a paradigm that challenges networks associated with craving (CR) and cognitive control (CCN). During the 12 weeks of opioid maintenance treatment, we will examine our primary clinical outcome, relapse (opioid use on >4 days per month and having an opioid positive urine screen), as well as days of opioid use.

2.c Inclusion/Exclusion Criteria:

UG3/UH3 Inclusion Criteria: (a) current opioid dependence, (b) between 21-50 years of age, (c) recent initiation of buprenorphine or methadone (<30 days)

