A priori task-based FMRI ROI analyses will be our primary method for quantifying changes in the craving, salience and cognitive control networks and subsequent hypothesis testing, while analyses involving the functionally defined ROIs will serve to validate our a priori findings. Mean task-related effect will be determined for each ROI of each individual for each condition of each task by averaging all voxels of each ROI. Results of these quantifications will be used as dependent measures in hypothesis testing. In primary analyses, mean effects will be examined across all nodes of each network, followed by analyses of each network node. Functional connectivity analyses will be performed on all networks during crosshair fixation (resting). We will use the seed region method. Briefly, BOLD signal will be averaged from four 3mm³ seed voxels at the center of mass of each ROI of each network (see Table 1) and extracted for each of the time points acquired. These reference series files will be used as predictors in one voxel-wise GLM analyses per ROI to identify the strength of the relationship between each brain voxel and the average of the seed region over time. Each a priori region will serve as a seed region once for its particular network. After Fischer's transformation from r-values to z-values, the resulting mean voxel-wise values will be averaged in each target node (i.e., ROI not serving as the seed) following each GLM. For CR, these target ROI averages will then be averaged across two seed region iterations (i.e., excluding the seed region; this step is not needed for the 2 ROI salience networks). The resulting means for the nodes of each network will be averaged across ROIs (3 for craving, 2 for salience, 3 for CCN) to derive a network coherence metric. Substance use type (heroin, prescription pills) will be included as a covariate in statistical models.

EEG analyses.

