Minimization. To minimize the risk of distress arising from the assessment procedure, only study staff that has been adequately trained in the assessment battery will complete all assessments, and senior study staff will supervise all assessment procedures. Individuals will also be advised that they may choose not to answer any question which they find upsetting. Further, during EEG and tDCS+CCN sessions, participants will be reminded they can stop the procedure at any time, if they get tired. All study procedures will be explained to the participants with an emphasis on the voluntary nature of the study. Furthermore, staff members will be trained to respect participants' wishes regarding their participation in the study or certain aspects of the study's procedure. There is minimal, if any, additional risk in having EEG data recorded; EEG is a safe and painless noninvasive technique that is routinely used in clinical medicine.

Benefits

Participants may benefit by feeling a reduction in their cravings for opiates. However, we cannot guarantee that they will benefit. The main benefits of this study are to help researchers and clinicians develop a better understanding of craving and substance use after starting opioid treatment.

7.b. Collection and reporting of AEs and SAEs

See 6.a

7.c Management of SAEs and other study risks

See 6.a and 7.a.

8. Trial Efficacy

8.a Plans for interim Analysis of efficacy data

Go/no go criteria for the UG3 phase will be demonstration of greater FMRI change in any node of the CR or CCN networks or enhanced frontal theta power during a WM task AND greater change in subjective craving measured during a cue reactivity task or outside the FMRI following the tDCS+CCN priming intervention compared to sham tDCS+CCN priming.

9. DSM Plan Administration

9.a Responsibility for data and safety monitoring

The Data Safety Monitoring Board will be comprised of 2 individuals independent from this research project. No member of the board will be a collaborator with the MPI on any other studies or have co-published with the MPIs in the past 3 years. They will be qualified to review the patient safety data generated by this study.

They will review rates of adverse events to determine any changes in participant risk and will make appropriate recommendations for changes in protocol, which will be submitted to the Butler Hospital IRB and NIDA for review.

9.b Frequency of DSM

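### Prespecifying days on buprenorphine or methadone as a covariate in the UG3 craving, fMRI and EEG models is a cheap gain in precision, not the repair of a bias

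*Combined protocol and SAP*

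**What the plan says.** Eligibility for both phases (2.c) requires "recent initiation of buprenorphine or methadone (<30 days", with no narrower window and no stated distribution of entry day. In UG3 (2.a, 2.b), "Participants in their first month of prescribed buprenorphine or methadone will be assessed using fMRI and EEG", once before tDCS and again about a week later, and they "will be randomized to tDCS+Cognitive Control Network (CCN) priming stimulation vs. sham tDCS+CCN priming". No stratification factor is described.

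The same section explains that sham is included "to separate the effects of ongoing opioid treatment from the effect of active tDCS on craving".

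The adjustments named are:
- **Go rule, craving limb (2.a, 2.b):** "greater change (at least 10% difference between conditions, controlling for baseline craving) in subjective craving". Baseline craving is the only covariate.
- **Go rule as given in 8.a:** "greater change in subjective craving measured during a cue reactivity task or outside the FMRI", with neither threshold nor covariate.
- **fMRI models (4.c):** 2x2 mixed ANOVAs, group by pre/post. "Substance use type (heroin, prescription pills) will be included as a covariate in statistical models".
- **EEG ANCOVA (4.c):** the baseline value of the outcome, plus any baseline variable that differs by arm or predicts attrition at p<0.05.

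Days on medication is named nowhere as a covariate. The treatment period that 2.a, 2.b says will be tracked for analysis is the span of the tDCS sessions, not time on medication.

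**The concern.** The outcome is a short-term change in people who may be a few days or nearly a month into a treatment that the plan itself expects to affect craving. Two people with equal baseline craving could have different expected changes over the next week because they are at different points on medication. If so, time on medication explains part of the variance in change, and leaving it out makes the arm contrast noisier than it need be.

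Precision matters in UG3 for two reasons. About 48 people decide whether the 100-person UH3 trial goes ahead, and UG3 is also meant to supply an effect size for active versus sham stimulation. The craving limb is the most exposed part of the go rule because it is a 10% threshold with no test attached, so no standard error stands between an unlucky allocation and the decision.

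**Working it through.** **Inputs from the documents (2.c, 2.d).** Entry at under 30 days; 60 enrolled, 20% loss, so 60 × 0.8 = 48, or 24 per arm; effect size 0.75; stated power 82%. Alpha and sidedness are not given.

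**Assumptions.** Entry is uniform over days 1 to 29. The correlation ρ between days on medication and change (after the adjustments already planned) is 0.1, 0.3 or 0.5. The documents give neither the distribution nor the correlation.

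**1. The plan's power figure.** A two-sample t-test with 24 per arm and d = 0.75 has power 0.820 at one-sided 0.05, which reproduces the 82%. At two-sided 0.05 it has 0.720. Both are carried forward.

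**2. Likely size of a chance imbalance.**
- SD of entry day = √[(29² − 1)/12] = √70 = 8.37 days.
- SE of the arm difference = 8.37 × √(2/24) = 2.4 days.
- 95% range = ±1.96 × 2.415 = ±4.7 days; expected absolute size = 2.415 × √(2/π) = 1.9 days.
- P(over 3 days) = 21%; P(over 5 days) = 4%.
- The EEG screen fires at about t(0.975, 46 df) × 2.415 = 4.9 days, so by construction it ignores about 95% of allocations.

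**3. Shift in the arm difference in change**, in SD of change: ρ × (imbalance in SE) × √(2/24).

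| ρ | at expected size | at 1.96 SE |
|---|---|---|
| 0.1 | 0.02 | 0.06 |
| 0.3 | 0.07 | 0.17 |
| 0.5 | 0.12 | 0.28 |

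The planned effect is 0.75 SD.

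**4. Sensitivity to the entry spread.** If entry ran only over days 1 to 15, the SD would be √(224/12) = 4.32 and the 95% range ±1.96 × 4.32 × 0.289 = ±2.4 days. With the slope per day held fixed, the 0.17 SD shift would become 0.17 × 4.32/8.37 = 0.09.

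**5. Error rates (100,000 simulated null trials).** Unadjusted two-sided type I error is 5.0% at ρ = 0.3 and 4.9% at ρ = 0.5, so there is no inflation overall. Among the roughly 4% of allocations with a 4 to 5.5 day imbalance in one given direction, it is about 7% (ρ = 0.3) or 12% (ρ = 0.5) two-sided. One-sided, in the direction that the imbalance pushes the estimate, it is about 12% or 21%. With the covariate all of these return to about 5%.

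**6. Power with the covariate.** The effective d is 0.75/√(1 − ρ²), with 45 df.

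| ρ | effective d | one-sided (from 0.820) | two-sided (from 0.720) |
|---|---|---|---|
| 0.1 | 0.754 | 0.823 | 0.724 |
| 0.3 | 0.786 | 0.850 | 0.760 |
| 0.5 | 0.866 | 0.905 | 0.835 |

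**7. The craving threshold.** The plan gives no scale or denominator for 10%. Reading it as 10 points on a point estimate, with SD of change 20, 30 or 40 points (all assumed), the chance of passing when tDCS has no effect is 1 − Φ{10/[SD × √(2/24)]} = 4%, 12% or 19%. Adjusting for a covariate with ρ = 0.3 lowers this only to 3.5%, 11% or 18%.

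**The case against.** A reader might infer that the go rule and imaging results are biased, so that a difference in medication timing could pass for a tDCS effect. The documents do not support that. Allocation is randomized and the sham arm is there to take out the effect of ongoing treatment. A leftover chance difference in entry day is ordinary sampling error, as for any unmodelled baseline variable, and step 5 shows type I error at about 5%. This part of the objection stands in full.

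Other points also stand. The size rests on assumed inputs. Much of the recruitment described in 3.a is through hospital programs, so entry days could cluster, which would shrink the shift. Control for baseline craving may already absorb part of any timing effect. Most of the craving limb's exposure comes from having a threshold without a test, which this covariate barely changes (step 7). The neural limb can be met through EEG theta, whose model could admit days on medication. Other unlisted variables, such as which medication is taken, are also candidates.

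These points limit the concern without removing it. On the natural reading, the craving limb must be met whichever neural measure succeeds, and it has no provision for this variable. The EEG screen acts only on extreme imbalances and ignores the precision to be had in a balanced trial. Days on medication has a particular claim because the plan itself says that ongoing treatment acts on craving and because eligibility already turns on it.

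**Conclusion.** The point holds as a low-cost improvement in precision. The plan leaves out a plausible prognostic covariate from the craving limb of the go rule and from the fMRI models, and makes its use in the EEG model depend on a significance screen. There is no systematic bias and no overall inflation of error. The loss is a modest amount of power (two-sided 0.720 against 0.724, 0.760 or 0.835 at ρ of 0.1, 0.3 or 0.5) and raised conditional error in the few allocations that are badly unbalanced. Even at the 95% limit of imbalance, the shift is 0.06 to 0.28 SD.

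The figures in days depend on uniform entry over days 1 to 29; those in SD units and the power gains depend on the assumed correlation. At ρ = 0.1 the gain is negligible.

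**What to change.** - **Data:** record the number of days from first buprenorphine or methadone dose to baseline assessment. The eligibility check implies that this is established, but the documents do not say that the number itself is kept, so name it as a data item.
- **Go rule:** in 2.a, 2.b and in 8.a, name this variable next to baseline craving, so that both statements carry the same covariates.
- **fMRI models (4.c):** add it next to substance use type.
- **EEG ANCOVA (4.c):** include it whatever the arm difference, with no significance screen.
- **Form:** fit it on the post value or on the change. Entered only as a between-subject main effect in a pre/post ANOVA, it would adjust the average of the two visits and leave the group-by-time contrast untouched.

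The cost is one degree of freedom per model, one recorded number and a few lines of text. The downside is little gain if timing is only weakly related to change. The missing test on the craving threshold needs its own remedy.

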Exclusion Criteria: (a) diagnosis of organic brain disorder, bipolar disorder, schizophrenia, schizo-affective, schizophreniform, or paranoid disorder, (b) current suicidality, (c) evidence of neurocognitive dysfunction, (d) contraindications for tDCS (e.g seizure disorder), (e) probation/parole requirements or an upcoming move that might interfere with protocol participation, (f) planning to terminate buprenorphine or methadone in less than 3 months, and (g) scalp lesions near the tDCS electrode sites.

Exclusion Criteria related to FMRI scanning are: (a) history of neurological disorder (e.g., epilepsy, stroke, brain injury with loss of consciousness>10 min), (b) impaired uncorrected vision, and (c) MRI contraindications (e.g., claustrophobia, specific metallic implants and injuries, and pregnancy).

tDCS-related considerations: Careful consideration will be given when determining whether tDCS is safe for potential participants. Additional exclusion criteria related to tDCS include: metal implanted in the cranial cavity, pacemaker, poor cognitive functioning (i.e., Alzheimer's disease or dementia), history of neurological disorder (e.g., epilepsy or other seizure disorder), or other significant or chronic medical conditions that affect the brain (e.g., Parkinson's disease, Huntington's disease, multiple sclerosis, traumatic brain injury). [name] will have the final decision regarding whether a participant is medically stable enough to engage in this trial.

2.d Power Calculation and Sample Size:

In the UG3 phase of this project, we plan to enroll 60 participants. With an expected attrition rate of 20% (data loss over two sessions due to poor performance or movement artifact—a conservative estimate that is a larger loss than in our ongoing FIRST study), our final sample size will be 48, or 24 per group. This number provides 82% power for the expected effect size of .75, chosen based on prior tDCS studies and our belief that a large effect size should be required to continue to the UH3. In the UH3 phase, we again anticipate a 20% attrition rate over the 5 tDCS sessions and initial two fMRI scans. If the third scan (at 4 weeks) is missed, we expect this will be due to treatment drop-out or relapse. With 100 participants enrolled, we will have a final sample of 80 patients which provides a power of .8 to detect a group difference in relapse between relapse and sham of 15% vs 39% at 3 months follow-up.

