1) CR: Two 2x2 mixed ANOVAs will be used to determine whether mean response to cues during CR decline across nodes of the craving network (VS, amygdala, VMPFC), including salience network (AI, ACC) and increases in the CCN (MFG, IPL). Significant pre-post main effects and group x treatment interactions are predicted in each. Those who received tDCS+CCN priming are expected to exhibit greater change. Follow up analyses of individual nodes within each network and whole-brain voxel-wise contrasts will be conducted to inform phase 2 analyses.

2) n-Back: Two 2x2 mixed ANOVAs will be used to determine whether mean response to the n-Back challenge increases across nodes of the CCN (MFG, IPL) and the salience network (ACC and AI). Significant pre-post main effects and group x treatment interactions are predicted in each. Those who received tDCS are expected to exhibit greater change. Follow up analyses of individual nodes within each network and whole-brain voxel-wise contrasts will be conducted to inform phase 2 analyses.

3) Resting state: Two 2x2 mixed ANOVAs will be used to determine whether mean network coherence (functional connectivity) decreases across nodes of the craving network (VS, amygdala, VMPFC), including the salience network (AI, ACC) and increases in the CCN (MFG, IPL). Significant pre-post main effects and group x treatment interactions are predicted

in each. Those who received tDCS are expected to exhibit greater change. Parallel exploratory analyses will be conducted to examine resting state functional connectivity of the salience network and DMN.

In the UH3, neuroimaging analyses will generally parallel those described for UG3. We will use a 2x3 ANOVA (three time points) to test the hypothesis that tDCS+CCN priming will be superior to sham tDCS+CCN priming on both subjective and fMRI measures of craving and cognitive control at the end of 5 sessions and at 3-months post tDCS. This same analytical method will be used to test the effect of intervention on days of drug use at the end of 5 sessions and at 3-months. We will use the Pearson χ^2 -test of independence to compare tDCS+CCN priming to sham tDCS+CCN priming on relapse at 3-months.

FMRI data analyses

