EEG outcome measures analyses. We will conduct a repeated-measures ANCOVA with a within-subject factor of time (baseline and end-of-stimulation (EOS)), between-subject factor of intervention condition (active tDCS and sham) and covariates to test if there is a statistically significant difference in in the EEG outcome (Δtheta) across treatment groups. Pearson correlations will be used to examine beta PSD values in relation to craving scores. A separate ANCOVA with the same factors will be used to explore treatment group differences in resting state EEG beta PSD values. Covariates for both analyses will include the baseline measure of the evaluated outcome, as well as baseline variables found to vary significantly ($p < 0.05$) by intervention arm, or which significantly ($p < 0.05$) predict attrition at EOS. Post-hoc t-tests will be used to probe anticipated significant interactions.

5. Quality Assurance

All research personnel, will have formal training in research with human subjects (e.g., CITI training, NIH Human Subjects training). Drs. [name], [name], and [name] will provide training to and supervise research assistants. Research assistants will also have training in Good Clinical Practice.

Drs. [name] and [name] will be responsible for quality control of this study. They will review recruitment and retention reports, and AE reports on a weekly basis. The MPIs (or their designee) will inspect BL documents (consent forms, release of information) for completeness within a week after they are signed. The MPIs (or their designee) will also conduct protocol and data quality monitoring twice a year using a checklist. This monitoring will include reviewing other study records to ensure completeness.

6. Regulatory Issues

6.a, 6.c Reporting of SAEs, Non-Medication Trials

Drs. [name] and [name] will be responsible for overseeing the daily safety of all participants. There are several ways in which they will become aware of adverse events. First, research staff will ask participants about serious adverse events (as defined by Office of Human Research Protections (OHRP); e.g., inpatient hospitalization) at each research contact point (UG3: baseline, week 2 assessment, 5 tDCS appointments, 2 fMRI; UH3: baseline,

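### The 82% UG3 power in section 2.d does not follow from 24 per group and an effect of 0.75 for a two-sided test at 0.05, which has 72%

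*Combined protocol and SAP*

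**What the plan says.** Section 2.d sets the UG3 sample size in three steps. Enrolment: "In the UG3 phase of this project, we plan to enroll 60 participants". Loss: "With an expected attrition rate of 20" per cent. Analysed sample: "our final sample size will be 48, or 24 per group". The power statement follows directly and refers to that analysed sample: "This number provides 82% power for the expected effect size of .75". The effect is described as an "expected effect size of .75, chosen based on prior tDCS studies and our belief that a large effect size should be required" for the trial to go on to the UH3. Nothing in 2.d gives the significance level, the sidedness, the test, the outcome, or the scale (follow-up, change or baseline-adjusted scores) on which 0.75 is measured.

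The tests themselves are in section 4.c. For the fMRI cue-reactivity task: "Two 2x2 mixed ANOVAs will be used to determine whether mean response to cues" fall in one set of regions and rise in another. The n-back and resting-state data get the same 2x2 mixed ANOVAs, and the EEG theta outcome gets a repeated-measures ANCOVA that includes the baseline measure. The hypotheses predict a direction, but no test is declared one-sided. The only 0.05 threshold in the document is for choosing EEG covariates, for example "baseline variables found to vary significantly ($p < 0.05$) by intervention arm".

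**The concern.** A power figure should be recoverable from the sample size, effect size and test given with it. Here the sample size and effect size are given, and the test can be taken from section 4.c. In a 2x2 mixed ANOVA, the group-by-time F test with 1 and 46 degrees of freedom is the same as a two-sided t test on change scores. At the usual 0.05 level these inputs do not give 82%.

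The figure describes how sensitive the UG3 phase is to the effect the sponsor regards as large enough to justify going on. If it is ten points too high, a non-significant UG3 test would be read as stronger evidence against that effect than 48 participants can supply.

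**Working it through.** **Inputs.** From section 2.d: n = 24 per group (60 × 0.8 = 48; 48 / 2 = 24) and effect 0.75. From section 4.c: group comparison by F tests with one numerator degree of freedom. Assumed, because the document does not say: alpha = 0.05, and 0.75 is a standardised mean difference (d) on the contrast tested.

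**Formula.** For two equal groups, the t statistic has df = 2n − 2 and noncentrality d × √(n/2). Power is the probability that this noncentral t exceeds the critical value; for a two-sided test the opposite tail adds a negligible amount.

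**Step 1: reproduce the stated figure.** df = 46 and noncentrality = 0.75 × √12 = 2.598. With the one-sided 0.05 critical value of 1.679, power is 82.0%. This matches the plan. It is equally a two-sided test at 0.10.

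**Step 2: the two-sided test.** Same df and noncentrality, critical value 2.013: power is 72.0%. The noncentral F with 1 and 46 df and noncentrality 0.75² × 12 = 6.75 gives the same 72.0%. The normal approximation gives 73.8%, so the choice of formula does not explain the gap of 82 − 72 = 10 points.

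**Step 3: another possible origin.** With all 60 enrolled (30 per group, df = 58, noncentrality 0.75 × √15 = 2.905), two-sided power is 81.5%, also close to the stated figure. The source of the 82% therefore cannot be settled from the number alone.

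**Step 4: what 24 per group can detect two-sided.** 80% power needs d = 0.826 (0.83 rounded); 82% needs d = 0.848.

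**Step 5: other readings of the 0.75.** Suppose 0.75 is the difference in raw follow-up scores, in SD units, and r is the correlation between baseline and follow-up. ANCOVA then works with d / √(1 − r²) and 45 df. A change-score analysis, which is what the 2x2 mixed ANOVA amounts to, works with d / √(2(1 − r)) and 46 df. Two-sided power with 24 per group:

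| r | ANCOVA | Change score |
|---|---|---|
| 0 | 72% | 44% |
| 0.3 | 76% | 58% |
| 0.4 | 79% | 64% |
| 0.5 | 84% | 72% |
| 0.6 | 89% | 81% |

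ANCOVA reaches 82% at r of about 0.47. The document gives no value of r.

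**The case against.** The strongest reply is that 72% is itself conditional. Section 2.d does not state alpha, sidedness or scale, and parts of the plan do adjust for baseline: the EEG ANCOVA in 4.c, and the craving element of the go/no-go criterion in section 2.a, 2.b. If 0.75 refers to raw follow-up scores, a baseline correlation near 0.47 would give 82% two-sided with 24 per group, and such a correlation is not implausible. This stands in part: it is a reason to call 72% conditional. It does not rescue the 82%, because 2.d claims no gain from adjustment and reports no correlation. On the same raw-score reading, the fMRI change-score ANOVAs would have less than 72% power at any correlation below 0.5.

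Two stronger readings are tempting, and the document supports neither. A reader might infer that the sponsor in fact used a one-sided test. That rests only on a numerical match, and step 3 shows a second origin that fits nearly as well.

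A reader might also infer that the chance of wrongly stopping after UG3 is 28% rather than 18%. It is not. The criterion in sections 2.a, 2.b and 8.a asks for greater change in any of several fMRI nodes, or enhanced frontal theta, together with a greater craving change (at least a 10% difference between conditions in 2.a, 2.b), and it names no significance threshold. The probability of meeting it follows from neither 72% nor 82%.

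It is also fair to say that the go/no-go rule does not use the power figure, so the practical weight is moderate.

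**Conclusion.** The concern holds in conditional form. With 24 analysed per group, a two-sided alpha of 0.05 (assumed) and 0.75 as the standardised difference on the contrast tested (assumed), power is 72.0% against a stated 82%. Reaching 82% needs a one-sided 0.05 (two-sided 0.10) test, an analysed sample of about 60, or a baseline-adjusted analysis of raw follow-up scores with a correlation of about 0.47. Section 2.d states none of these, and its wording ties the figure to 48. The arithmetic is firm; which unstated assumption produced the 82% cannot be determined. The conclusion concerns the power of a single test and says nothing about the probability of passing the UG3 gate.

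**What to change.** Replace the power sentence in section 2.d with: *With 24 per group and a two-sided alpha of 0.05, a two-group comparison with a standardised difference of 0.75 on the tested contrast has 72% power; the difference detectable with 80% power is 0.83.* Name the outcome and test to which this applies.

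If a one-sided test or a gain from baseline adjustment was intended, declare and justify it in 2.d, giving the assumed correlation in the second case, and make the analysis in 4.c match.

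The cost is one sentence and a less favourable stated figure. No extra enrolment is asked for, and if the two-sided statement is adopted the analysis does not change.
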